3.3.4 Rescreening of Patients

Not applicable.

3.3.5 Early Termination of Study/ Site

This study may be terminated at any time by Lupin if any safety concerns arise, or inability to achieve recruitment. In this event, Lupin will inform about the decision along with reason to the study Investigators, Institutions, ECs and all applicable regulatory authorities. The study may be terminated by the sponsor if new scientific knowledge becomes available that makes the objectives of the study no longer feasible or scientifically and ethically invalid.

In such cases, patients will be continued on/shifted to appropriate alternate therapy by the Investigator.

4 TREATMENT OF PATIENTS AND INVESTIGATIONAL PRODUCT MANAGEMENT

4.1 Treatment of Patients

4.1.1 Dosage and Treatment Regimen

Mexiletine will be used at the discretion of the treating physician without protocol mandated instructions or limitations.

Patients should take the study medication as prescribed by the investigator, preferably with food and at the same time daily.

For patients who are not able to swallow capsules, capsule contents to be opened and sprinkled on food or mixed with milk/juice. Details on dosing, formulation, route and mode of administration will be collected by the caregiver in the electronic data capture (EDC).

Each patient/caregiver will be provided with sufficient prescriptions until next clinically indicated study visit.

4.1.1.1 Dose Escalation

Any dose escalation -or reduction- will be at the discretion of the treating physician and will be duly collected in the CRF.

4.1.1.2 Stopping rules

Treatment will be permanently discontinued immediately if one of the following criteria is

met:

- Ventricular tachyarrhythmia
- Complete heart block (i.e. third-degree atrioventricular block) or any heart block susceptible to evolve to complete heart block (first-degree atrioventricular block with markedly prolonged PR interval (≥ 200 ms) and/or wide QRS complex (≥ 120 ms), second-degree atrioventricular block, bundle branch block, bifascicular and trifascicular block),
- QT Interval \geq 450 ms
- Myocardial infarction (acute or past), or abnormal Q-waves
- Symptomatic coronary artery disease
- Heart failure with ejection fraction <50%
- Atrial tachyarrhythmia, fibrillation or flutter
- Sinus node dysfunction (including sinus rate < 50 bpm)

In case of permanent discontinuation of the study medication, details of reason for discontinuation must be documented in the CRF and every attempt should be made to complete the EOT assessments.

Medical monitor will perform a comprehensive review and evaluation of the events and will make a decision as to the continuation of recruitment, dosing as well as in the trial.

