3.3 Selection of Study Population

3.3.1 Inclusion Criteria

- 1. Male or female patients from birth to less than 6 years
- 2. A genetically confirmed diagnosis of NDM or DM (DM1or DM2), as per the treating clinician.
- 3. Presence of clinical symptoms of myotonia (hand grip myotonia, myotonia in the leg muscles, any other myotonia symptoms) to be confirmed by the treating clinician.
- 4. Patients already receiving mexiletine treatment or who are clinically considered for mexiletine treatment as per the treating physician judgement.
- 5. No history of or significant cardiac abnormalities as determined by a cardiologist's assessment of the ECG and echocardiogram performed prior to enrolment in the study or as per the treating physician standard of care (NaMuscla SmPC, 2023)
- 6. No known history or signs and symptoms of any significant liver disorder as per treating physician.
- 7. No known clinically relevant abnormal laboratory investigations for haematology, biochemistry, and urinalysis values at screening (or based on values obtained within 3 months prior to screening in patient's medical record) that could affect the study objectives as judged by the treating physician.
- 8. Parent or legal guardian able to provide assent to study participation and to sign the written informed consent prior to study entry and perform any study-related activity.

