3.3.2 Exclusion Criteria

- 1. Any contraindication to mexiletine as listed in the Namuscla Summary of Product Characteristics (SmPC) (NaMuscla SmPC, 2023)
 - a) Hypersensitivity to the active substance, or to any of the excipients
 - b) Hypersensitivity to any local anaesthetic
 - c) Ventricular tachyarrhythmia
 - d) Complete heart block (i.e., third-degree atrioventricular block) or any heart block susceptible to evolve to complete heart block (first-degree atrioventricular block with markedly prolonged PR interval (≥ 200 ms) and/or wide QRS complex (≥ 120 ms), second-degree atrioventricular block, bundle branch block, bifascicular and trifascicular block),
 - e) QT interval > 450ms
 - f) Myocardial infarction (acute or past), or abnormal Q-waves
 - g) Symptomatic coronary artery disease

- h) Heart failure with ejection fraction <50%
- i) Atrial tachyarrhythmia, fibrillation or flutter
- j) Sinus node dysfunction (including sinus rate < 50 bpm)
- k) Co-administration with medicinal products inducing torsades de pointes.
- 1) Co-administration with medicinal products with narrow therapeutic index
- 2. Any other neurological or psychiatric condition that might affect the study assessments, as per the treating clinician.
- 3. Any clinically significant illness, laboratory findings, ECG, or other clinical symptoms, which in the opinion of the treating physician could affect the patient's optimal participation in the study
- 4. Receiving strong inducers or inhibitors of CYP2D6 or CYP1A2 or planned to receive them, during the subject participation (See section 4.1.5.1 Prohibited medications)
- 5. Any concurrent illness, or medications which could affect the muscle function, and confound the results according to the treating physician.
- 6. Seizure disorder, diabetes mellitus requiring treatment by insulin.

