5.1 Screening Visit – V0 (Maximum 2 weeks)

The screening procedures will include recording the following parameters which typically have already been collected in the patient's medical history:

- 1. Obtaining written informed consent/ assent as per regulatory requirement
- 2. Patient demographics and anthropometric measurements (age, gender, ethnicity, height, weight)
- 3. Vital signs, including blood pressure (BP), heart (pulse) rate (HR)
- 4. Current medical condition: Type of myotonic disorder (genetic diagnosis), age of symptom onset, family history of myotonic disorders.
- 5. Signs and symptoms of myotonia as documented in medical history.
- 6. Clinical myotonia evaluation appropriate to patient's age and treating physicians standard clinical practice including proposed efficacy assessments and quality of life evaluations, where performed.
- 7. Review of inclusion/exclusion criteria
- 8. Medical history of:
 - Neurological disorders (Seizure, Epilepsy, Vertigo, Headache, Paraesthesia, Dysgeusia, Ataxia)
 - Gastrointestinal disorders (Abdominal pain, Nausea, Vomiting, Diarrhoea, Constipation, Intestinal ulcer, GI bleeding, Dysphagia, Oesophageal ulceration)
 - Renal or hepatic disorders
- 9. Any other significant medical history
- 10. History of unprovoked falling and stumbling, fractures
- 11. History of swallowing difficulties and/or laryngospasm (particularly below 6 months of age) / history of aspirations/ aspirational pneumonia (myotonia of mastication muscles)
- 12. History of hospitalisation due to muscle condition
- 13. History of any cardiac, rhythm disorders.
- 14. Cardiac status at baseline (ECG and echocardiogram (cardiac ultrasound; US), done up to 3 months prior to screening is acceptable. If not done earlier, ECG and echocardiogram to be performed at screening visit)
- 15. Surgical history
- 16. For patients previously prescribed mexiletine, any modification in mexiletine dose/ frequency in addition to the current dose/frequency as prescribed by the treating physician

- 17. History of previous anti-myotonia treatment other than / mexiletine
- 18. Concomitant medications in use (along with dose and frequency)
- 19. Washout for any current/ ongoing medications required/not required
- 20. Collection of known laboratory investigations if performed according to the treating physician regular practice including basic haematology, biochemistry and urinalysis.

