All AE records should contain AE term/ AE diagnosis, date of onset, severity, relationship to the study drug, outcome, date of recovery or outcome, action taken with the study drug, action taken with AE, AE leading to discontinuation of patient from study and whether the event is classified as serious.

The investigator must continue to follow-up the patient with all AEs regardless of the causal relationship to the study drug until the AE has resolved or until the condition stabilizes to an acceptable level or is determined to pose no issue, or until follow-up is no longer feasible.

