8.2 Adverse Events of Special Interest (AESI)

Adverse events, which are considered by the investigator to be a neurological disorder or gastrointestinal in nature, will be recorded as an adverse event of special interest.

All subjects should be carefully monitored for the diagnosis of listed AEs of special interest. All AEs of special interests should be evaluated properly and their relationship with the study drug should be recorded

Severe Cutaneous Adverse Reactions (SCARs)

Mexiletine is contraindicated in patients with known hypersensitivity to mexiletine, or to any of the excipients or to any local anaesthetic, as there is possibility of occurrence of potentially lethal severe cutaneous adverse reactions, usually severe cutaneous eruption along with fever, lymphadenopathy, hypereosinophilia, lymphocytosis or organ damage (notably liver and kidney).

Cardiac Arrhythmia

Mexiletine is a class I b antiarrhythmic drug according to the Vaughan Williams classification, and as such, it may induce an arrhythmia or accentuate a pre-existing arrhythmia, either diagnosed or undiagnosed. Mexiletine should be administered with caution in patients with pre-existing cardiac conduction anomalies. The advent (under mexiletine therapy) of an atrioventricular block, a permanent complete heart block, or a sinoatrial block necessitates the interruption of the mexiletine treatment.

Increased Frequency of Seizure Episodes in Patients with Epilepsy

Common elements of pathogenesis create a basis for the assumption that antiarrhythmic drugs may affect seizure phenomena and interact with antiepileptic drugs.

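### The QT limits for entry and for stopping overlap at 450 ms: a treated child with that value is eligible and must also stop mexiletine permanently

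*Protocol*

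**What the plan says.** **Entry.** Exclusion 1 reproduces the mexiletine contraindications and presents them as those of the Namuscla SmPC. Item 1e reads "QT interval > 450ms", identically in the synopsis and in section 3.3.2.

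**Stopping.** Section 4.1.1.2 says "Treatment will be permanently discontinued immediately if one of the following criteria is" met, and then lists eight cardiac conditions. The QT item is "QT Interval \geq 450 ms".

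**Who can be enrolled, and on which ECG.** Inclusion 4 (section 3.3.1) admits "Patients already receiving mexiletine treatment or who are clinically considered for mexiletine treatment". Section 5.1, item 14, says that an ECG and echocardiogram "done up to 3 months prior to screening is acceptable".

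**Rate correction.** Neither the exclusion, the stopping rule nor section 8.5 (ECG assessments) says whether QT is corrected for heart rate.

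**The concern.** The two limits differ in whether 450 ms itself is included. For a child already on mexiletine, the value that passes entry also requires treatment to end at once and permanently.

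This matters because section 4.1.1 otherwise leaves mexiletine use to the treating physician. The stopping list is one of the few binding treatment instructions in the protocol, it applies to children from birth, and it is to be acted on immediately. A site that meets the overlap has two fixed limits giving opposite answers and no text that ranks them.

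**Working it through.** No sample size, power or error rate is involved, so the check sets the two lists side by side.

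**1. Pairing exclusions 1c to 1j (section 3.3.2) with the eight items in 4.1.1.2**

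| Exclusion | Subject | Limit at entry | Limit for stopping | Same? |
|---|---|---|---|---|
| 1c | Ventricular tachyarrhythmia | presence | presence | yes |
| 1d | Heart block | PR ≥ 200 ms, QRS ≥ 120 ms for first degree | PR ≥ 200 ms, QRS ≥ 120 ms for first degree | yes |
| 1e | QT | > 450 ms | ≥ 450 ms | **no** |
| 1f | Infarction or Q-waves | presence | presence | yes |
| 1g | Coronary disease | symptomatic | symptomatic | yes |
| 1h | Heart failure | EF < 50% | EF < 50% | yes |
| 1i | Atrial arrhythmia | presence | presence | yes |
| 1j | Sinus node | rate < 50 bpm | rate < 50 bpm | yes |

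Seven of the eight pairs agree and one differs. The stopping list is plainly modelled on the exclusions, which suggests that the QT difference was not intended.

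**2. Size of the overlap**

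- Eligible on criterion 1e: QT ≤ 450 ms.
- Must stop under 4.1.1.2: QT ≥ 450 ms.
- Both: QT = 450 ms only. At every other value the two rules agree.

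**3. Whether it can happen**

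Inclusion 4 allows a child to be on mexiletine at entry. Item 14 of section 5.1 allows the baseline ECG to predate screening by up to 3 months. The entry ECG can therefore be an on-treatment ECG. A treated child with a QT of 450 ms passes criterion 1e and meets the stop criterion.

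**4. Rate correction (a secondary clarification, not a mismatch)**

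Both rules say QT without qualification, so on this they agree. The open question is what 450 ms refers to. The beat interval in ms is 60,000 / heart rate. Setting it to 450 gives 60,000 / 450 = 133.3 bpm. At that rate an uncorrected QT of 450 ms would fill the whole beat. The protocol gives no heart rates for its patients, so it is an assumption that many infants have rates in this region.

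**The case against.** **The overlap is one value, and the stricter rule is the safe one.** This stands. If a site stops treatment at 450 ms, no child is exposed to added cardiac risk, and the conflict vanishes at any other value. It is the reason for the low grading.

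**Entry at 450 ms is not automatic.** Inclusion 5 asks for no significant cardiac abnormality, on a cardiologist's assessment or by the physician's standard of care. Exclusion 3 lets the physician exclude on an ECG finding. Both are matters of judgement, however, and do not reconcile two fixed numerical limits.

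**The stopping rule may not be meant for an ECG taken before enrolment.** Section 4.1.1.2 does not say that it is, so applying it to the entry tracing is an inference. The conflict does not depend on it: a QT of 450 ms on the first on-study ECG of a treated child triggers the stop, although the same value allowed entry.

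**The sign may be misread.** In the extracted text the stopping-rule sign appears as a typesetting code, while PR and QRS in the same section show the ordinary symbol. The same code stands for a genuine greater-or-equal sign in the age bound of the FLACC item, so a misreading is unlikely. A look at the PDF settles it.

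**A stronger reading: section 8.2 also conflicts with the stopping list over heart blocks.** A reader might infer this, because 8.2 says that an atrioventricular block, a permanent complete block "or a sinoatrial block necessitates the interruption of the mexiletine treatment", while 4.1.1.2 speaks of permanent discontinuation and does not name sinoatrial block. The document does not support it:

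- Second-degree and complete block are on the 4.1.1.2 list.
- Sinoatrial block reads naturally under "Sinus node dysfunction (including sinus rate < 50 bpm"), where the bracket illustrates and does not exhaust the item.
- First-degree block with PR below 200 ms and QRS below 120 ms is a category that the protocol never shows to exist.
- Interruption does not exclude a permanent stop.
- Section 3.3.3 leaves discontinuation for an adverse event to the investigator or sponsor, and 4.1.1.2 gives the medical monitor the review of events and of dosing.

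**Conclusion.** The contradiction is real and confined to QT = 450 ms: one of eight paired criteria, at one value. Severity is minor. How many children would be affected cannot be derived, because the protocol gives no QT distribution.

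The effect on the analysis is small. Section 6.1 counts adverse events leading to discontinuation and treatment interruptions among the primary variables, so a stop forced by the rule could appear there. But each adverse event record holds the "action taken with the study drug" (section 8.1.3), so the data show what was done. The analysis is descriptive, and no test depends on it.

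The missing statement on rate correction applies equally to both rules. A reader might infer that the limit is uncorrected and therefore useless in infants. The protocol does not say that it is uncorrected; it leaves the matter open. The 133 bpm figure is exact arithmetic, but its relevance rests on assumed heart rates.

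**What to change.** Use one inequality in both places. The preferred change is in section 4.1.1.2, to QT > 450 ms. It alters one sign and leaves exclusion 1e as it stands, in the list presented as that of the SmPC. If the sponsor wants the stricter limit, use QT ≥ 450 ms in the synopsis, section 3.3.2 and section 4.1.1.2, and note that 1e then departs from the list it says it reproduces.

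In the same amendment, state in all three places that the limit applies to rate-corrected QT and name the formula. The choice of formula is for the sponsor's cardiac advisers.

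The cost is a wording amendment under section 10.3, with no added visit, procedure or patient. A site that reports only the measured QT would calculate the corrected value from the same tracing.

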1.2 Rationale

Mexiletine hydrochloride (CAS ID: 5370-01-4) is a class 1b anti-arrhythmic agent, based on the Vaughan Williams classification, with local anaesthetic properties, similar in structure and activity to lidocaine (lignocaine) and flecainide. As described in the Ph. Eur. Monograph (2008), mexiletine hydrochloride is a white or almost white, crystalline powder. It exhibits polymorphism. It is freely soluble in water and in methyl alcohol; sparingly soluble in dichloromethane. A 10% solution in water has a pH of 4.0 to 5.5.

[figure not shown]

Figure 1 Chemical Structure of Mexiletine HCl (Source: ChemID Plus)

Mexiletine was initially developed as a treatment for ventricular arrhythmias with subsequent use in long QT syndrome (Heatwole *et al.*, 2013; Sarret *et al.*, 2024). However, after the marketing withdrawal of Boehringer Ingelheim's Mexitil[®] (indication: ventricular arrhythmias) in 2009, there was a significant shortage of supply of licensed mexiletine products in the EU. The originator product was withdrawn from the market because newer active substances superseded the use of mexiletine in the treatment of ventricular arrhythmias.

Despite the shortage, mexiletine gained acceptance as an effective anti-myotonia therapy in both dystrophic and non-dystrophic myotonia (that is, for both the chloride and sodium channelopathies) (Kwiecinski *et al.*, 1992; DGN, 2012; Heatwole *et al.*, 2013; Sarret *et al.*, 2024). Some availability of mexiletine for treatment of myotonic disorders was based on a named patient basis although often associated with supply issues. Therefore, based on the unmet need and the strong evidence for use of mexiletine for treatment of myotonic disorders, an application for marketing authorisation was submitted by the centralised procedure in June 2017 and approved for use throughout the EU in December 2018. Namuscla® containing mexiletine HCl as active substance is currently indicated for the symptomatic treatment of myotonia in adult patients with non-dystrophic myotonic disorders.

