3.3.3 Withdrawal of Patients

In accordance with the Declaration of Helsinki and the informed consent form, patients may discontinue the study at any time without any penalty or loss of benefits to which the patient is otherwise entitled. For all patients withdrawn from the study, efforts will be made to ascertain the reason for withdrawal.

A withdrawn patient is one who meets any of the following withdrawal criteria stated below and whose study participation is discontinued. The reasons for patient withdrawal will be recorded in the case report form, signed, and dated at the last assessment visit.

Criteria for Withdrawal from Study

A patient may be withdrawn from the study due to any of the following withdrawal criteria:

- A patient's desire/ or guardian decision to withdraw for any reason (withdraws consent)
- Lost to follow-up (every effort must be made to contact the patient; the effort to contact must be documented in the Investigator's file)
- Inability of patient to comply with the Protocol for any reason
- The patient needs emergency treatment or is unable to continue participation in the trial due to the exacerbation of symptoms.
- If in the Investigator's opinion that continuing the patient in the trial is not appropriate, the Investigator may withdraw a patient at any time if it is considered to be in the patient's best interest.
- Withdrawn patients will be replaced to comply with the agreed minimum number of patients with PDCO.

Criteria for Treatment Discontinuation

• An adverse event, which in the opinion of the Investigator and/or Sponsor, necessitates discontinuation of treatment.

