8.1.3 Recording and Collection of Adverse Events

It is the responsibility of the investigator to collect all AEs (both serious and non-serious) derived from spontaneous, unsolicited reports of patients, by observation and by routine open questions.

AE reporting will extend from date of informed consent until completion of the final visit (EOT). Any ongoing AE at end of study visit should be followed until the outcome is evident and resolved, clinically stabilized or a plausible explanation has been found.

Pre-existing diseases (before participating in the study) are not considered to be AEs, unless the disease worsens during the study period. Concomitant diseases prior to enrolment will be recorded in the eCRF.

Signs and symptoms clearly associated with the disease under study (including symptoms of disease progression) should be reported as AEs if they are newly emergent (i.e., findings not previously observed in the patients), or are determined by the investigator as severe or a worsening, or if the investigator considers deterioration of disease-related signs and symptoms to be caused directly by the study drug.

Abnormal laboratory values/ ECGs/ vital signs/ ophthalmic/ physical and systemic examination should be reported as AEs *only* if the Investigator considers the abnormality as clinically relevant or significant or believes that the abnormality should be reported as an AE.

Any dose (and associated symptoms) given to the patient that exceeds the dose prescribed to the patient has, at a minimum, to be recorded as a non-serious AE in the patient file and CRF/ eCRF. Any case of overdose leading to an AE or SAE should be reported to Medical Monitor according to reporting requirements. In case of an accidental overdose, the patient should be monitored by the Investigator for any adverse clinical events, as deemed necessary by the Investigator.

After completion of all visit assessments, the Investigator must document any AEs arising from these assessments. In case of an SAE, the Investigator must also complete an SAE report form and report it to safety contact, as described in Section 8.1.4.2 Relationship to the Study Drug.

All AEs will be recorded in case report form (eCRF) regardless of the causal relationship to the study drug.

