8.5 Electrocardiogram Assessments (ECGs)

A 12-lead ECG will be performed at screening and after screening according to regular clinical practice or at the discretion of the treating physician. Any abnormal findings will be evaluated for clinical significance.

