8.8 Sample Size

The number of patients, and type of study, was agreed with the paediatric committee (PDCO) during paediatric investigation plan (PIP) review. A total of at least 10 paediatric evaluable patients in cohorts 1 and 2. At least 4 patients from birth to less than 6 months (cohort 2) and at least 6 patients from 6 months to less than 6 years (cohort 1).

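### The only numeric QT stop (450 ms) and the matching exclusion carry no rate correction in a study enrolling from birth, so this one criterion loses sensitivity as heart rate rises

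*Protocol*

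**What the plan says.** Section 4.1.1.2 of the protocol introduces its list of eight stopping criteria with "Treatment will be permanently discontinued immediately if one of the following criteria is" met. The third criterion is a QT interval of 450 ms or more, and it is the only QT criterion in the list. The other numeric limits there concern PR, QRS, ejection fraction and sinus rate.

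Exclusion 1e, in the Synopsis and in section 3.3.2, is "QT interval > 450ms". Exclusion 1 presents its items as contraindications from the Namuscla product label. Section 1.2 describes that product as "indicated for the symptomatic treatment of myotonia in adult patients with non-dystrophic myotonic disorders". The study enrols from birth to under 6 years, and section 8.8 requires at least 4 infants under 6 months and at least 10 children in all.

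No section mentions QTc, a correction formula, or a QT limit by age or heart rate. Section 8.5 says of ECGs: "Any abnormal findings will be evaluated for clinical significance". It leaves ECGs after screening to routine practice or the physician's discretion.

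**The concern.** QT shortens as heart rate rises, so a fixed limit on the measured interval becomes harder to reach at faster rates. A limit listed for adults may work tolerably at slow rates and poorly at fast ones, and this study is confined to young children.

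The sponsor chose a QT stop that takes effect without weighing by the investigator. Section 1.3 supports the risk-benefit case partly by saying that arrhythmia risk is watched through ECGs. Dosing has no protocol limit (section 4.1.1), so the mandatory stops are the main fixed constraint on treatment. If the QT stop weakens with heart rate, children with the same corrected QT are treated differently according to how fast the heart was beating when the ECG was taken.

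There is also a small mismatch of sign. Entry is barred above 450 ms, but treatment stops at 450 ms or above.

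**Working it through.** **Inputs from the protocol:** the stop at QT of 450 ms or more (section 4.1.1.2) and the exclusion at QT above 450 ms (Synopsis and section 3.3.2, item 1e). The protocol derives no QT figure, so there is none to reproduce.

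**Assumed:** heart rates of 80 to 160 bpm, with 60 bpm as the reference. The protocol gives no paediatric heart rates.

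**Formulas:** beat length RR = 60000/HR in ms. With RR in seconds, Bazett QTc = QT/√RR and Fridericia QTc = QT/RR^(1/3).

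**Step 1: where the limit equals a whole beat.** RR = 450 ms when HR = 60000/450 = 133.3 bpm. Above that rate, a QT of 450 ms would have to outlast the beat.

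**Step 2: what a measured QT of 450 ms means at each rate.**

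| HR (bpm) | RR (ms) | 450/RR | QTc Bazett (ms) | QTc Fridericia (ms) |
|---|---|---|---|---|
| 60 | 1000 | 45% | 450 | 450 |
| 80 | 750 | 60% | 520 | 495 |
| 100 | 600 | 75% | 581 | 534 |
| 120 | 500 | 90% | 636 | 567 |
| 140 | 429 | 105% | 687 | 597 |
| 160 | 375 | 120% | 735 | 624 |

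For example, at 120 bpm Bazett gives 450/√0.5 = 636 and Fridericia gives 450/0.5^(1/3) = 567. The measured limit equals a QTc of 450 ms only at 60 bpm.

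**Step 3: the formula has to be named.** For any one QTc limit, the measured QT that meets it under Bazett, divided by the one under Fridericia, is RR^(1/6). This is 0.953 at 80 bpm and 0.849 at 160 bpm, so Bazett triggers at a measured QT 5% to 15% shorter.

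**Step 4: the sign.** A child measured at exactly 450 ms is not excluded by 1e but meets the permanent stop at once. No other reading is affected.

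**Step 5: what else could stop treatment for a long QT.** Section 8.2 says that a new block "necessitates the interruption of the mexiletine treatment", but that covers atrioventricular and sinoatrial block, not QT. Section 8.1.3 makes an abnormal ECG an adverse event only "if the Investigator considers the abnormality as clinically relevant or significant" or otherwise thinks it should be reported. Section 3.3.3 provides for stopping on "An adverse event, which in the opinion of the Investigator and/or Sponsor, necessitates discontinuation of treatment". Each of these QT routes depends on opinion.

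**The case against.** The protocol never says the QT is uncorrected. It is silent, and clinicians may correct as a matter of habit. But the text as it stands names a plain interval with no formula, and nothing in it implies a correction. If sites did correct, step 3 shows that they could apply different rules.

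The stronger objection is that many safeguards surround this criterion. Ventricular tachyarrhythmia, the heart blocks and sinus node dysfunction are separate mandatory stops. Exclusion 3 covers clinically significant ECG findings, and drugs that induce torsades de pointes are barred. Section 4.1.1.2 also has the medical monitor review events and decide on dosing and recruitment. Section 1.3 says the label's extra cardiac monitoring after dose increases has been applied. All of this stands, and it confines the gap to one criterion of eight. None of it supplies a QT limit that works at fast rates.

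A reader might infer that the youngest children have no QT protection, or that the stop can never act in Cohort 2. The documents do not support that: they give no heart rates, so the number of children above 133 bpm cannot be derived, and the judgement-based routes remain open. A reader might also infer damage to the safety endpoint. A judgement-based stop for an adverse event would still be recorded and counted as one leading to discontinuation, so the weakness lies in the safety rule and not in the endpoint.

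The sign mismatch is close to editorial, because it touches a single value.

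**Conclusion.** The concern holds as a badly set safety rule. Read as written, the only numeric QT stop and its matching exclusion become less sensitive as heart rate rises. At an assumed 80 to 120 bpm they act only at a QTc of about 520 to 636 ms (Bazett) or 495 to 567 ms (Fridericia), and above 133 bpm they cannot in practice be met. The conversions are exact; how often they matter rests on heart rates that the protocol does not state. The loss is already visible at 80 bpm, so the conclusion does not need any child to exceed 133 bpm. Cardiac protection is reduced, not absent. Endpoints, sample size and analysis are unaffected.

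**What to change.** **Section 4.1.1.2.** Keep the stop at QT of 450 ms or more. Add a QTc stop using one named correction formula and one paediatric limit, both agreed with a cardiologist and written into the protocol before first enrolment. Apply it to every ECG taken. When the limit is reached, have the tracing re-measured to rule out error; if the value stands, stopping is mandatory. That keeps the new rule from falling back on opinion. The documents support no particular formula or limit, so the cardiologist agreement has to supply both.

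**Synopsis and section 3.3.2.** Leave 1e as label text. Add a study-specific exclusion for QT of 450 ms or more, or QTc at or above the new limit. This also prevents a child at exactly 450 ms from being enrolled and then stopped at once.

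**Cost.** Wording in three places and one agreement with a cardiologist. QTc is calculated from ECGs already taken, and section 3.1 allows extra safety measures within the observational design. A few more children may be excluded or stopped, which is noticeable when the minimum is 4 in Cohort 2 and 10 overall, but section 3.3.3 provides for withdrawn patients to be replaced. A child stopped after a dose taken under consent stays in the Safety Population (section 8.12). The rule can act only on ECGs that are actually taken, because section 8.5 leaves those after screening to routine practice.
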